4.5.1.5 Monitoring of Dose Administration

In prior experience with MEDI0382, there has been 1 injection-site reaction and no anaphylactic reactions. During visits to the clinical unit, the site of administration will be checked for signs of injection-site reaction as required

As with any exogenous peptide or biologic product, allergic reactions to dose administration are possible. Therefore, appropriate drugs and medical equipment to treat acute anaphylactic reactions must be immediately available at the study sites where the first 5 doses will be administered, and study personnel must be trained to recognize and treat anaphylaxis.

4.5.2 Additional Study Medications

Additional medications that may be used during the study, and management of their dose and potential toxicities, is discussed in Section 3.1.4.

4.5.3 Labelling

Labels for the investigational product will be prepared in accordance with Good Manufacturing Practice (GMP) and local regulatory guidelines. Label text will be translated into local languages, as required.

4.5.4 Storage

All investigational product should be kept in a secure place under appropriate storage conditions. The label on the investigational product kit specifies the appropriate storage.

4.5.5 Treatment Compliance

Investigational product is administered at the study site by study site personnel for the first four doses, who will monitor compliance. Thereafter, study site personnel should monitor compliance through verbal report and drug accountability at each study visit.

4.5.6 Accountability

The investigator's or site's designated investigational product manager is required to maintain accurate investigational product accountability records. Upon completion of the study, copies of investigational product accountability records will be returned to MedImmune. All unused investigational product will be returned to a MedImmune-authorized depot or disposed of upon authorization by MedImmune or designee.

4.6 Treatment Assignment and Blinding

4.6.1 Methods for Assigning Treatment Groups

An IXRS will be used for randomisation to a treatment group and assignment of blinded investigational product kit numbers. A subject is considered randomised into the study when the investigator notifies the IXRS that the subject meets eligibility criteria and the IXRS provides the assignment of blinded investigational product kit numbers for the subject.

Subjects will be randomised using a 1:1 ratio to receive either MEDI0382 or placebo. Sufficient subjects will be invited to participate in the study such that in total approximately 40 subjects will be randomised and 20 will complete dosing in the active arm and 20 will complete dosing in the placebo arm. [REDACTED]

The first dose of investigational product (MEDI0382 or placebo) must be administered the same day the investigational product is assigned, within 4 hours after the investigational product is assigned. If there is a delay in the administration of investigational product such that it will not be administered within the specified timeframe, the study monitor must be notified immediately.

4.6.2 Methods to Ensure Blinding

This is a double-blind study in which MEDI0382 and placebo PFS titration volumes are not identical/indistinguishable in appearance. Neither the subject nor any of the investigator or sponsor staff who are involved in the treatment or clinical evaluation of the subjects will be aware of the treatment received (ICH E9).

The different fill volumes of investigational product (MEDI0382 and placebo) and the relative position of the plunger rods will be visually distinct during administration. To maintain the blind, investigational product (MEDI0382 and placebo) PFS will be handled by an unblinded investigational product manager or unblinded study personnel that will not be involved in the treatment or clinical evaluation of subjects. An unblinded qualified designee may administer investigational product to subjects during in-clinic visits. An unblinded site monitor will perform investigational product accountability, and this will be a different person to the blinded site monitor who will oversee other aspects of the study at the clinical site (see Section 6.2). The site will maintain a written plan detailing which staff members are blinded/unblinded and the process of investigational product administration used to maintain the blind.

In the event that treatment allocation for a subject becomes known to the investigator or other study staff involved in the management of study subjects, the sponsor must be notified *immediately*.

4.6.3 Methods for Unblinding

4.6.3.1 Unblinding in the Event of a Medical Emergency

In the event of a medical emergency, the investigator may unblind an individual subject's investigational product allocation. Instructions for unblinding an individual subject's investigational product assignment are contained in the IXRS manual. In general, unblinding should only occur if management of the medical emergency would be different based on the investigational product administered to the subject. If the management of a medical emergency would be the same whether or not MEDI0382 was received by the subject, the treatment assignment should not be unblinded.

MedImmune retains the right to unblind the treatment assignment for SAEs that are unexpected and are suspected to be causally related to an investigational product and that potentially require expedited reporting to regulatory authorities.

If a subject's investigational product allocation is unblinded to the blinded site staff or blinded MedImmune/contract research organization (CRO) trial team, the subject should be discontinued from investigational product.

4.7 Restrictions During the Study and Concomitant Treatment(s)

The investigator must be informed as soon as possible about any concomitant medication taken from the time of screening until the end of the study (final study visit). Any concomitant medication(s), including herbal preparations, taken during the study will be recorded in the eCRF.

4.7.1 Permitted Concomitant Medications

Investigators may prescribe concomitant medications or treatments deemed necessary to provide adequate supportive care except for those medications identified as "excluded" as listed in Section 4.7.2. Specifically, subjects should receive full supportive care during the study, including transfusions of blood and blood products, and treatment with antibiotics, anti-emetics, anti-diarrheals, and analgesics, and other care as deemed appropriate, and in accordance with their institutional guidelines.

4.7.2 Prohibited Concomitant Medications

Other than the medications described above, use of herbal supplements is not permitted. Subjects must be instructed not to take any medications, including over-the-counter products, without first consulting with the investigator.

- Concurrent or previous use of a GLP-1 analogue containing preparation within the last 30 days or 5 half-lives of the drug, if known, whichever is longest, at the time of Visit 2
- Concurrent use of any herbal preparations or medicinal products licensed for control of body weight or appetite and within 1 week prior to the start of dosing (Visit 4)
- Concurrent or previous use of drugs approved for weight loss (eg, orlistat, bupropion-naltrexone, phentermine-topiramate, phentermine, lorcaserin) and within the last 30 days or 5 half-lives of the drug, whichever is longest, prior to the start of dosing (Visit 4)
- Concurrent use of opiates, domperidone, metoclopramide, or other drugs known to alter gastric emptying and within 2 weeks prior to the start of dosing (Visit 4)

- Concurrent use of aspirin (acetylsalicylic acid) at a dose greater than 150 mg once daily and within the last 3 days prior to the start of the run-in period (Visit 2)
- Concurrent use of paracetamol (acetaminophen) at a total daily dose greater than 3000 mg and within the last 3 days prior to the start of the run-in period (Visit 2)
- Concurrent use of ascorbic acid (vitamin C) at a total daily dose of > 1000 mg and within the last 3 days prior to the start of the run-in period (Visit 2)

4.8 Statistical Evaluation

4.8.1 General Considerations

Tabular summaries will be presented by treatment group. Categorical data will be summarized by the number and percentage of subjects in each category. Continuous variables will be summarized by descriptive statistics. Additional details of statistical analyses will be described in the statistical analysis plan. Analyses of secondary and exploratory efficacy variables will be performed without any adjustment for multiplicity.

Analysis Populations

Intent to Treat: The intent-to-treat (ITT) population is defined as all subjects that are randomised and receive any amount of investigational product, analysed according to randomised treatment assignment. All efficacy analyses will be performed on the ITT population unless otherwise specified.

As-Treated Population: The as-treated population is defined as all subjects who received at least 1 dose of investigational product and will be analysed according to the treatment actually received. All safety analyses will be performed on the as-treated population.

PK Population: The PK population includes all subjects who received at least 1 dose of investigational product and had at least one PK sample taken with a value above the lower limit of quantitation.

Immunogenicity Population: The Immunogenicity population includes all subjects in the as-treated population who have at least one serum immunogenicity result.

4.8.2 Sample Size

Forty subjects (20 completers in the MEDI0382 group and 20 completers in placebo group) will provide > 85% power to detect 18.1% difference between the two treatment groups in percentage change in the MMTT glucose AUC from baseline (Day -5) to the end of 32 days of treatment (Day 32), with a two-sided significance level of 0.1 and assuming the standard deviation of 20%.

4.8.3 Efficacy

4.8.3.1 Primary Efficacy Analysis

The primary efficacy analysis will be performed using the ITT population. The primary efficacy endpoint, percentage change in MMTT glucose AUC from baseline (Day -5) to the end of 32 days of treatment will be analysed using an analysis of covariance (ANCOVA) model. The model will include fixed effect of treatment and baseline AUC as a covariate. The difference of the percent change in glucose AUC between the two treatment arms will be compared with a two-sided significance level of 0.10.

4.8.3.2 Secondary Efficacy Analyses

Secondary efficacy analyses will be performed using the ITT population. All secondary efficacy endpoints will be summarised by visit and by treatment group. The change in percentage of time spent within a target glucose range of 70 mg/dL (3.9 mmol/L) to 180 mg/dL (10 mmol/L) over a 7-day period at baseline to the final week of treatment will be analysed using a Wilcoxon rank-sum test. All other continuous endpoints will be analysed using a similar ANCOVA model as that for the primary analysis.

4.8.4 Safety

4.8.4.1 Analysis of Adverse Events

Adverse events will be coded using the Medical Dictionary for Regulatory Activities (MedDRA) by system organ class (SOC) and preferred term (PT). Specific AEs will be counted once for each subject for calculating rates, but will be presented in total in subject listings. In addition, if the same AE occurs multiple times within a particular subject, the highest severity and level of causality will be reported. If any associations of interest between AEs and baseline characteristics are observed, additional stratified results may be presented. All treatment-emergent AEs will be summarized overall and by MedDRA SOC and PT, by severity and relationship to investigational product. In addition, summaries of deaths, SAEs and treatment discontinuations due to AEs will be provided.

4.8.4.2 Analysis of Clinical Laboratory Parameters

Laboratory parameters will be assessed at baseline as well as throughout the study. Frequencies of abnormal laboratory measurements will be presented for each laboratory parameter. Also, laboratory parameters will be assessed by presenting tables containing information related to laboratory shifts from baseline relative to the normal range, as well as descriptively over time.

4.8.5 Analysis of Immunogenicity/Pharmacokinetics

4.8.5.1 Pharmacokinetic Analyses

Pharmacokinetic parameters such as maximum concentration (C_{max}), time to maximum observed concentration (T_{max}), and AUC_{tau} , will be estimated from plasma concentration-time data for MEDI0382 at the [REDACTED] dose level if data permit. Descriptive statistics will be generated for PK parameters for the MEDI0382 group at [REDACTED] and for C_{trough} at each dose level. Subjects who have at least one measurable concentration time point of investigational product will be used for this analysis.

4.8.5.2 Immunogenicity Analyses

The incidence and impact of ADA to MEDI0382 will be evaluated. The number and percentage of subjects with confirmed positive serum antibodies to MEDI0382 will be reported by dose level.

4.8.6 Additional Analyses

4.8.6.1 Vital Signs Analyses

The change in the 24-hour average systolic BP, diastolic BP, and pulse rate from the ABPM will be summarized for each post-baseline evaluation. Vital signs (blood pressure, pulse rate, temperature and respiration rate) will be summarized at each visit.

4.8.6.2 ECG Analyses

Frequencies of abnormal ECGs and descriptive statistics of changes in ECG variables heart rate and RR, PR, QRS, QT, and QTc intervals will be summarized.

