4.1.3 Exclusion Criteria

Any of the following would exclude the subject from participation in the study:

- 1 History or presence of significant medical or psychological conditions, including substance dependence/abuse, or significant abnormalities in laboratory parameters or vital signs including ECG, which in the opinion of the investigator, would compromise the subject's safety or successful participation in the study. As an example, severe anaemia (haemoglobin < 7.0 g/dL) could be exclusionary due to blood sampling required by the protocol, at the discretion of investigator.
- 2 Concurrent participation in another interventional study of any kind and repeat randomisation in this study is prohibited
- 3 Any subject who has received another investigational product as part of a clinical study or a GLP-1 analogue-containing preparation within the last 30 days or 5 half-lives of the drug (if known; whichever is longer) at the time of Visit 2
- 4 Any subject who has received any of the following medications within the specified timeframe prior to the start of the study (Visit 2) (see Section 4.7.2 for further details)
 - Herbal preparations within 1 week prior to the start of dosing (Visit 4) or drugs licensed for control of body weight or appetite (eg, orlistat, bupropion-naltrexone, phentermine-topiramate, phentermine, lorcaserin) within 30 days (or 5 half-lives of the drug) prior to the start of dosing (Visit 4)
 - Aspirin (acetylsalicylic acid) at a dose greater than 150 mg once daily and within the last 3 days prior to the start of the run-in period (Visit 2)
 - Paracetamol (acetaminophen) or paracetamol-containing preparations at a total daily dose of greater than 3000 mg and within the last 3 days prior to the start of the run-in period (Visit 2)
 - Ascorbic acid (vitamin C) supplements at a total daily dose of greater than 1000 mg and within the last 3 days prior to the start of the run-in period (Visit 2)
 - Opiates, domperidone, metoclopramide, or other drugs known to alter gastric emptying and within 2 weeks prior to the start of dosing (Visit 4)
- 5 Severe allergy/hypersensitivity to any of the proposed study treatments or excipients
- 6 Symptoms of acutely decompensated blood glucose control (eg, thirst, polyuria, weight loss), a history of type 1 diabetes mellitus or diabetic ketoacidosis
- 7 Subjects who have undergone a renal transplant

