4.1.6 Discontinuation of Investigational Product

An individual subject will not receive any further investigational product if any of the following occur in the subject in question:

- 1 Withdrawal of consent from further treatment with investigational product
- 2 Lost to follow-up
- 3 An AE that, in the opinion of the investigator or the sponsor, warrants discontinuation of further dosing; specific examples include:
 - Dose-limiting symptoms with respect to GI tolerability and in particular if a subject requires intravenous fluids to treat volume depletion secondary to nausea and vomiting, even after measures are taken to reduce the risk of vomiting, after discussion with the medical monitor
 - $eGFR \leq 25 \text{ mL/min/1.73 m}^2$ on two consecutive blood tests
 - Acute kidney injury (AKI) in a subject as defined by:
 - An increase in serum creatinine by 0.3 mg/dL (26.5 $\mu\text{mol/L}$) within 48 hours in at least 2 readings
 - An increase in serum creatinine to 1.5 times baseline in at least 2 readings, which is known or presumed to have occurred within the prior 7 days
 - Subject noncompliance that, in the opinion of the investigator or sponsor, warrants withdrawal (eg, refusal to adhere to scheduled visits).
 - Pregnancy in a female subject
 - Subjects with persistent fasting glucose level of $> 260 \text{ mg/dL}$ (14.4 mmol/L) despite a MTD of rescue therapy to enable optimisation of the subject's glycaemic control
 - Any subject where Hy's Law criteria on liver function tests is met: AST or ALT $\geq 3 \times$ ULN **together with** Total bilirubin $\geq 2 \times$ ULN
 - Any subject who develops a life-threatening arrhythmia including sustained ventricular tachycardia, ventricular fibrillation or new ECG changes of second or third-degree heart block

Subjects who are permanently discontinued from receiving investigational product will be followed for protocol-specified assessments including follow-up of any AEs unless consent is withdrawn from further study participation (Section 4.1.5), the subject is lost to follow-up, the subject starts alternative treatment, or the subject is enrolled in another interventional clinical study.

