3 STATISTICAL METHODS

3.1 General Considerations

Data will be presented in data listings sorted by insulin strata, treatment, subject number and date collected, where appropriate. Tabular summaries will be presented for each treatment and for insulin strata within treatment. Categorical data will be summarized by treatment and for insulin strata within each treatment with the number and percentage of subjects within each category. In general, continuous variables will be summarized by treatment and insulin strata within treatment with descriptive statistics including mean, standard deviation, median, minimum, and maximum. Safety variables will generally be summarized by treatment across insulin strata.

All available data will be included in the analyses and missing data will not be imputed except as specified in the calculation of the AUC values. Unless specified otherwise, baseline values will be defined as the last valid assessment prior to the first administration of study medication.

All statistical tests will be 2-sided at an alpha = 0.10 significance level unless stated otherwise. There will be no adjustment for multiplicity.

Data analyses will be performed using SAS[®] version 9.3 or higher (SAS Institute Inc., Cary, NC) in a UNIX environment. The analytical results generated from SAS programs will follow MedImmune SAS programming standards and will be validated according to MedImmune SAS validation procedures.

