3.5.4 Clinical Laboratory Evaluation

Hematology, serum chemistry, and urinalysis laboratory evaluations will be performed during the study. The hematology and serum chemistry (including calcitonin, lipase, and amylase) parameters as well as their changes from baseline will be summarized with descriptive statistics (number of subjects, mean, and standard deviation, median, minimum and maximum) by insulin strata and treatment group. Other laboratory parameters collected will be summarized in a similar manner. The hematology and serum chemistry results will also be classified as low, normal, or high. The urinalysis results will be classified as normal or abnormal. The shift from baseline hematology, serum chemistry, and urinalysis results will be summarized by insulin strata and treatment at each evaluation time.

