3.5.5.3 Electrocardiogram

Electrocardiogram parameters will be assessed with a single ECG at each evaluation (Screening, Days 1, 5, 12, 19, 32 40 and 60) using a digitally recorded standard 12-lead electrocardiograph. The ECG parameters: Heart rate, RR, PR, QRS and QT intervals as well as derived parameter QT corrected interval QTcF (Fridericia's formula $\frac{QT}{\sqrt[3]{RR}}$) will be summarized. The results at each evaluation as well as the change from baseline (Day 1) for each post-baseline evaluation will be descriptively summarized by insulin strata and treatment. For the qualitative variable ECG interpretation, the ECG Interpretation results will be summarized with frequencies and percentages at each evaluation.

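### The planned ECG tables cannot count subjects with a new abnormality by arm; add a shift table from Day 1 and counts of QTcF outliers (low severity, free improvement)

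*Protocol*

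**What the plan says.** Protocol 4.8.6.2 plans "Frequencies of abnormal ECGs and descriptive statistics of changes in ECG variables heart rate and RR, PR, QRS, QT, and QTc intervals". It does not say whether the frequencies are by visit or relative to baseline.

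SAP 3.5.5.3 is more specific and treats two kinds of ECG data differently:

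- **Numeric parameters** (heart rate, RR, PR, QRS, QT, QTcF): the result at each evaluation is summarised, and the "change from baseline (Day 1) for each post-baseline evaluation will be descriptively summarized by insulin strata and treatment". SAP 3.1 defines the usual content as "descriptive statistics including mean, standard deviation, median, minimum, and maximum".
- **Qualitative interpretation**: "the ECG Interpretation results will be summarized with frequencies and percentages at each evaluation". No change or shift from Day 1 is mentioned.

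For laboratory data, SAP 3.5.4 says: "The shift from baseline hematology, serum chemistry, and urinalysis results will be summarized by insulin strata and treatment at each evaluation time". In the same section urinalysis is classified only as normal or abnormal. Protocol 4.8.4.2 also plans laboratory shift tables.

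On entry, exclusion criterion 1 in Protocol 4.1.3 covers significant abnormalities in laboratory values or "vital signs including ECG, which in the opinion of the investigator, would compromise" safety or participation. The exclusion list contains no QTc limit.

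**The concern.** ECG is one of the named secondary safety measures (Protocol 2.2, Table 2). The natural question is how many subjects on each arm developed an abnormality they did not have before dosing. A table of abnormal tracings at each visit mixes findings present at entry with findings that arose on treatment, and a new abnormality in one subject can be offset by a reversion in another. The entry rule allows both to occur.

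The sponsor already uses the right tool for a variable of the same kind: urinalysis, coded normal or abnormal, gets a shift from baseline. Neither document explains why ECG interpretation does not.

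A smaller, parallel gap affects QTcF. The descriptive statistics give location, spread and extremes, but neither document plans a count of subjects beyond any value or any rise.

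**Working it through.** The plan states no ECG figure to reproduce, so the check is what can and cannot be recovered from the planned tables.

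**Inputs.** n = 20 per arm (Protocol 4.8.2; 1:1 allocation in Protocol 4.6.1). The documents give no baseline rate of abnormal ECGs, so the counts below are assumptions shown over a range. Interpretation is taken as two categories, normal and abnormal.

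**1. New abnormalities at one visit.** Let b be the number abnormal at Day 1 and m the number abnormal at a later visit. The number newly abnormal is then known only to lie between max(0, m − b) and min(m, n − b).

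| b | m | Newly abnormal, range | At risk (20 − b) | Upper end as share of those at risk |
|---|---|---|---|---|
| 2 | 2 | 0 to 2 | 18 | 2/18 = 11% |
| 4 | 4 | 0 to 4 | 16 | 4/16 = 25% |
| 6 | 6 | 0 to 6 | 14 | 6/14 = 43% |
| 8 | 8 | 0 to 8 | 12 | 8/12 = 67% |
| 4 | 6 | 2 to 6 | 16 | 6/16 = 38% |

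In the first four rows the table would show an unchanged frequency, whatever happened within subjects. The number newly abnormal is fixed by the table only when the two bounds meet, for example when nobody is abnormal at baseline.

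**2. Ever abnormal after baseline.** Separate visit frequencies do not give this either. With 2 of 20 abnormal at each of two visits, the number abnormal at least once is between 2 (the same subjects) and 2 + 2 = 4 (different subjects).

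**3. QTcF.** Suppose one subject has a rise of 60 ms and the others do not change. The mean moves by 60/20 = 3 ms in an arm of 20, or 60/10 = 6 ms in an assumed insulin stratum of 10. The mean therefore says little, but the planned maximum change would print 60 ms. The maximum does not give the number of subjects: the same maximum is compatible with one subject or several beyond any lower limit.

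**4. Comparison with laboratory data.** Urinalysis and ECG interpretation can both be read as normal or abnormal at repeated visits. SAP 3.5.4 crosses the first with baseline; SAP 3.5.5.3 does not cross the second.

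**The case against.** The strongest reply is that serious ECG findings have other routes into the report.

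- Protocol 5.1 makes an ECG finding an adverse event if it needs intervention or is judged medically significant, and treatment-emergent events are tabulated by arm.
- Protocol 4.1.6 stops dosing for life-threatening arrhythmia, including "new ECG changes of second or third-degree heart block", and discontinuations due to adverse events are summarised.
- SAP 3.1 adds subject-level data: "Data will be presented in data listings sorted by insulin strata, treatment, subject number and date collected, where appropriate".

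This stands, and it limits the point. What escapes the summary tables is mainly new abnormality that the investigator judged neither significant nor in need of intervention. Listings hold the information but do not compare the arms.

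Three stronger readings are tempting, and the documents do not support them:

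- A reader might infer that individual QTc outliers are concealed because only means are reported. SAP 3.1 includes the minimum and maximum, so an extreme value or rise is visible.
- A reader might infer that a baseline imbalance between arms would pass for a drug effect. SAP 3.5.5.3 lists Screening and Day 1 among the evaluations, so the table itself shows the imbalance.
- A reader might infer that abnormal entry ECGs will be common. The documents give no rate, and exclusions 13 and 14 remove several recent cardiac conditions and severe heart failure.

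It is also fair to say that vital signs and ambulatory blood pressure get no shift tables, that table templates sit in a separate programming plan which is not available here, and that no test or decision rule depends on the ECG tables. Vital signs and ambulatory pressure are numeric, however, so their change from baseline can be summarised directly; a normal or abnormal reading needs a cross-tabulation. Templates in the programming plan may add one, but the SAP does not call for it.

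**Conclusion.** The point holds in a limited form. As written, the ECG interpretation summary cannot give the number of subjects newly abnormal in each arm, and no count of subjects beyond a QTcF limit is planned. With 2 to 8 of 20 abnormal at both Day 1 and a visit, the number newly abnormal is undetermined between 0 and that same count. Those baseline counts are assumed. The conclusion that the number is not identified needs only that some subjects are abnormal at baseline and some at the visit, which the entry rule permits.

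This is a free improvement of low severity. The documents do not support saying that outliers are concealed, that only means are reported, or that a baseline imbalance would go unseen. The primary analysis, sample size and power are unaffected.

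**What to change.** In SAP 3.5.5.3, with a matching line in Protocol 4.8.6.2, add by treatment:

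1. A shift table of ECG interpretation from Day 1 predose to each later visit and to the worst post-baseline evaluation. Its normal-at-baseline row gives the number newly abnormal and the correct denominator.
2. Counts of subjects in QTcF value and change-from-Day 1 categories. The sponsor should set the cut-offs before unblinding; the documents give no basis for choosing them here.

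The text should also say which tracing counts at each visit. Table 10, footnote f, requires a predose and a 2-hour post-dose ECG on Days 1 and 32, whereas SAP 3.5.5.3 describes a single ECG at each evaluation. The Day 1 post-dose tracing should not be taken as baseline.

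The cost is a few sentences and two tables from data already collected, with no extra ECGs. The SAP is written to Protocol Amendment 2 while the protocol is now at Amendment 4, so the change can be made when the SAP is next brought into line.
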